4.5 Unscheduled visits

We do not anticipate having unscheduled visits. Study staff may speak with participants over the phone outside of scheduled visits should participants have questions about the study, their participation, or experience any adverse events during their study participation

4.6 Concomitant Medication documentation

Data will be collected regarding participants' pain medication use at the baseline and post-intervention assessments. As this study is a behavioral intervention trial and other types of medication are not of importance for the research, we do not anticipate needing to document other concomitant medications.

4.7 Rescue medication administration (if applicable)

Not applicable

4.8 Subject Completion/ Withdrawal procedures

Subject Completion: Participants' enrollment in the study will be considered complete once the intervention sessions have ended, post-test measures and phone interview are complete, and study compensation provided. Should participants not complete the post-test survey or phone interview, their participation will be complete when the window to complete such assessments has passed and they have been compensated for any completed study procedures.

Subject Withdrawal: Should a participant choose to withdraw from the study for any reason, their withdrawal will be documented in the case report form (**see Appendix D**) and they will be provided with any study compensation that may still be pending based on completed study procedures. Should any adverse event occur during study enrollment that prohibits a participant from completing study procedures, the participant will be withdrawn from the study and provided with any study compensation that may still be pending based on completed study procedures.

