1.3 Non-Clinical and Clinical Study Findings

Potential benefits: Studies indicate that mindfulness-based interventions such as MBSR may have a number of pain-related and psychological benefits for individuals with chronic pain of mixed etiologies. In studies of CNCP, mindfulness intervention have been shown to reduce depression^{22,23}, anxiety, perceived stress, and pain perception²³ and improve quality of life²², physical functioning¹², and pain acceptance.²⁴

Potential risks: Based on results of previous literature, we expect there to be no more than minimal risk in this study; however, literature on MBSR has not systematically included adverse event reporting, although most studies have not reported any serious risk from participating in MBSR. There have been reports of increased emotional distress and increased awareness of both positive and negative experiences, which may initially increase distress when participants are not used to directing attention towards unpleasant thoughts, feelings, and sensations. ²⁵ The MBSR curriculum guide by [name] notes the potential for increased negative emotions at the beginning of the course, as well as the possibility that history of trauma, abuse, recent loss, or substance addiction could heighten negative emotional reactions. With an experienced instructor, reactions can be managed and appropriate referrals made. ²⁵

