3.4 Study Population

Participants will be patients in UNC Clinics that assist with pain management, including but not limited to the Department of Anesthesiology Pain Clinic, the Spine Center, Physical Medicine and Rehabilitation, and Internal Medicine.

Inclusion Criteria

- 1. Adults aged 18 and older
- 2. Diagnosed with one or more CNCP conditions (daily pain for at least 3 months duration)
- 4. Established with one or more physician providers for pain management (e.g. primary care physician, pain specialist, etc).
- 5. Report more than minimal pain bothersomeness (>3 on 0-10 scale) and/or pain interference with activities (>2 on a 0-10 scale).
- 6. Able to read, understand and speak English

Exclusion Criteria

- 1. Diagnosis of mental illness with psychotic features
- 2. History of inpatient admission for psychiatric disorder in past 2 years
- **3.** Active substance abuse within the past year
- **4.** Has completed an MBSR or other mindfulness course; has or previously had a regular mindfulness meditation practice.
- **5.** Unable or unwilling to comply with study procedures (online questionnaires and practice diaries, 4 weekly intervention sessions, home practice, and one semi-structured phone interview).

4 STUDY PROCEDURES (what will be done)

See **Appendix A** for the schedule of evaluations.

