4.4 Follow- up procedures (by visits)

Post-Test Questionnaires: After the final intervention session (week 4), participants will be emailed a link with a REDCap survey containing all of the questionnaires from the

baseline survey, excluding demographic information. It will also include questions on intervention credibility.

Post-Test Interview: With-in 1 to 2 weeks after the final session, participants will be scheduled for a 15 to 30-minute semi-structured phone interview with the PI to assess participants' experience with the intervention sessions and overall study. Questions will address the following: satisfaction and usefulness of the skills and content, acceptability of the format, any challenges, and any suggestions for improvement of the intervention or study procedures.

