6.5 Interim Analysis

We are not planning any pre-specified interim analyses for any reason. The study may be suspended by the PI if a serious adverse event occurs that is deemed to be secondary to our intervention. We do not expect any serious adverse events given the low risk of this study.

7 STUDY INTERVENTION (drug, device or other intervention details)

The mindfulness intervention will consist of four, weekly group mindfulness skills sessions each lasting 1 hour and 30 minutes. Each session will have approximately 85 minutes of intervention material scheduled, with time for a 5-minute break in the middle. Sessions will be co-instructed by PI [name] and faculty advisor [name]. All sessions will take place at the same UNC clinic or conference room location on a weekday or week-night. Participants will receive guided audio recordings for mindfulness skills practice, in addition to a binder with course handouts. Participants will be asked to practice for up to 30 minutes daily and to log their practice in the home practice questionnaires that will be emailed and completed using REDCap surveys. Home practice questionnaires will ask about which mindfulness skills were practiced and the number of minutes practiced. Participants will be asked to attend all four sessions as is possible and session attendance data will be collected and evaluated.

Mindfulness skills taught will include sitting meditation with mindfulness of breath, thoughts, emotions, or physical sensations; body scan meditation; walking meditation; and mindfulness of routine daily activities. Mindfulness training involves the intentional self-regulation of attention towards a specific aspect of present-moment experience (e.g. the breath, physical sensations, thoughts, emotions, sounds) while noticing and releasing cognitive fixation on thoughts and emotions about the past or future, or judgments and resistance towards present-moment experience. Didactic content will be presented and discussed amongst the group, with content focusing on topics such as defining mindfulness and how it can help with stress and pain management, the difference between mindfulness and being on autopilot, stress and its relationship to chronic pain, how our perceptions affect stress, the relationship between pain and distressing thoughts and emotions, acceptance of pain and unwanted experiences, using mindfulness in daily life. See **Appendix B** for session-by-session content and home practice assignments.

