APPENDIX A.
Schedule of Evaluations

Assessment	Phone Screening	Consent: Online form	Pre-test: Online Survey	Treatment Visit 1 (Week 1)	Treatment Visit 2 (Week 2)	Treatment Visit 3 (Week 3)	Treatment Visit 4 (Week 4)	Post-test: Online Survey	Post-test: Phone Interview
Inclusion/Exclusion Criteria	Х								
Informed Consent Review and Form	х	Х							
Feasibility: Enrollment, retention, attendance, data collection	х	Х	х	х	х	х	х	х	х
Acceptability: Satisfaction, barriers, suggestions to improve intervention								х	х
Demographics, pain conditions/regions			Х						
Instructor fidelity to intervention protocol				х	Х	х	Х		
Daily home practice and pain intensity/interference (exploratory outcomes)				х	X (daily from W1- 2)	X (daily from W2- 3)	X (daily from W3- 4)		
Pain medication usage			Х					Х	
Secondary outcomes: PROMIS outcomes, psychological variables			х					х	
Credibility Questionnaire					Х				
Adverse Reactions/Events				х	Х	Х	Х		

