Appendix B. Measures

Scale or Item	Description
Screening Measures/Items	
Drug Abuse Screening Test ²⁷ (DAST)-10	10 items; assess drug use in the past 12 months
Alcohol Use Disorders Identification Test	3 items; assesses alcohol consumption, drinking
(AUDIT) ^{28,29}	behaviors, and alcohol-related problems
Chronic pain	Have you experienced pain on a daily basis for at least
	3 months?
Pain bothersomeness	How bothersome was your pain in the previous week?
	(rating scale 0-10).
Pain interference with general activities	How much did your pain interfere with your general
	activities in the past week? (rating scale 0-10).
Diagnosis of mental illness with psychotic	Have you ever been diagnosed with schizophrenia,
features	schizoaffective disorder, or another psychiatric
	disorder with psychotic symptoms?
Psychiatric hospitalization in past 2 years	Have you ever been hospitalized for mental health
	reasons? When was the last hospitalization?
Previous mindfulness training	Have you ever participated in mindfulness training or
	course? Have you ever had a regular mindfulness
	practice? When?
Baseline-only Measures	
Demographic variables	Age, race/ethnicity, education, income, marital status
Pain conditions and regions	e.g. fibromyalgia, osteoarthritis, low-back pain,
	migraine, neck pain, etc
Baseline and Post-test Measures*	
Pain Medication Use	Pain medications taking, frequency, and dose
Physical Function (short-form 4a) ³⁰	4 items; difficulty with activities of daily living
Anxiety (sf 4a)	4 items; suggestive of anxiety in the past 7 days
Depression (sf 4a)	4 items; suggestive of depressed mood in past 7 days
Sleep Disturbance (sf 4a)	4 items; sleep quality and disturbance in past 7 days
Pain Interference (sf 6b)	6 items; degree to which pain interferes with life
Pain Intensity	1 item; average pain intensity past 7 days (0-10)
Positive Affect and Wellbeing	9 items;
Perceived Stress Scale – 4	4 items; global measure of perceived stress
Pain Catastrophizing Scale ³¹	13 items; 3 subscales characterizing thoughts and
	feelings when in pain – rumination, magnification,
	helplessness
Chronic Pain Acceptance Questionnaire ³²	20 items; acceptance of experiencing pain
Freiberg Mindfulness Inventory	14 items; measures all aspects of mindfulness
Intervention Satisfaction	1 likert-type item asking how satisfied are with the
2.22	intervention oveall
Credibility Questionnaire ^{34,35} (after session	5 items assessing opinions about the intervention

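### Section 4.8 can be read as withdrawing a participant from the whole study, and so from the post-test survey and interview, when an adverse event stops only the sessions or home practice

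*Combined protocol and SAP*

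**What the plan says.** Section 4.8 sets the rule for adverse events: "Should any adverse event occur during study enrollment that prohibits a participant from completing study procedures, the participant will be withdrawn from the study". The participant is then paid for whatever was completed. The same section treats people who merely fail to return the post-test survey or do the interview differently: "their participation will be complete when the window to complete such assessments has passed".

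Section 4.8 does not define study procedures. The only place that lists them is exclusion criterion 5 in Section 3.4: "study procedures (online questionnaires and practice diaries, 4 weekly intervention sessions, home practice, and one semi-structured phone interview".

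Section 6.1 makes acceptability part of the primary outcome, measured by the credibility questionnaire and by an interview on satisfaction, barriers and improvements. In Appendix A the row "Acceptability: Satisfaction, barriers, suggestions to improve intervention" is marked only at the post-test online survey and the post-test phone interview. Appendix B puts the satisfaction measure ("1 likert-type item asking how satisfied are with the" intervention) in the baseline and post-test group. Section 4.4 has the interview cover satisfaction and usefulness, "acceptability of the format, any challenges, and any suggestions for improvement of the intervention or study procedures".

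**The concern.** The rule is mandatory, and withdrawal is from the study, not from the sessions. If study procedures include the sessions and home practice, a participant who can no longer do those, but could easily answer an online survey and take a 15 to 30 minute call, is withdrawn. No section provides for any post-test assessment after withdrawal. Such a person therefore supplies no satisfaction rating and no interview.

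Acceptability is a primary outcome, and the interview exists partly to learn what keeps people from engaging. Someone who had to stop because of an adverse event can speak directly to that, at least where the event had something to do with the course. The situation is foreseeable: Section 1.3 reports that the MBSR curriculum guide "notes the potential for increased negative emotions at the beginning of the course". That is a possibility, not a forecast, and the section adds that an experienced instructor can manage such reactions.

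**Working it through.** **1. The texts side by side**

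- Section 4.8: withdrawal is compulsory when an event prevents completing study procedures.
- Section 3.4, criterion 5: study procedures include the four sessions and home practice as well as questionnaires, diaries and interview.
- Section 9: withdrawal is one example of action after an adverse event, taken if needed.
- Section 4.4 and Appendix A: satisfaction, barriers and suggestions come only after session 4.
- Credibility: after session 2 in Appendices A and B, but in the post-test survey in Section 4.4.

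On the listing in Section 3.4, an event that stops only sessions or home practice triggers withdrawal. Sections 4.8 and 9 do not agree on whether that is automatic.

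**2. Timing**

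With weekly sessions on days 0, 7, 14 and 21, and post-test contacts up to two weeks after the last, those contacts fall on days 21 to 35. That is 21 to 35 days after session 1 and 14 to 28 days after session 2. An early event could have settled by then.

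**3. The plan's own figures (Section 6.4)**

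- Retention: 1.96 × √(0.85 × 0.15 / 24) = 0.143, against 0.14 stated.
- Number at post-test: 24 × 0.85 = 20.4, against 20 stated.

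Both reproduce. This point disputes neither.

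**4. How many people**

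The documents give no rate for such events. Assume a chance p per person, independently, among 24. The chance of at least one is 1 − (1 − p)^24, and the expected number is 24p.

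| p (assumed) | At least one | Expected number |
|---|---|---|
| 1% | 21% | 0.24 |
| 2% | 38% | 0.48 |
| 5% | 71% | 1.2 |
| 10% | 92% | 2.4 |

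These are upper limits on interviews lost through the rule, because some affected people would decline anyway.

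**5. Effect on a satisfaction percentage**

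Assume 85% of 20 completers are satisfied, and k people stopped by an event are left out, each satisfied with chance s. Others missing are ignored. The overstatement is k / (20 + k) × (0.85 − s).

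| k | s = 0 | s = 0.50 | s = 0.85 |
|---|---|---|---|
| 1 | 4.0 points | 1.7 | 0 |
| 2 | 7.7 points | 3.2 | 0 |

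The 95% half-width at n = 20 is 1.96 × √(0.85 × 0.15 / 20) = 0.156, about 16 points. Even if all four planned dropouts (24 − 20) were of this kind and none was satisfied, the figure would be 4/24 × 0.85 = 14.2 points, still under the half-width.

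**6. Effect of the remedy on retention**

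Keeping one such person in the study can add 1/24 = 4.2 points. Because 20/24 = 83.3% and 21/24 = 87.5%, one person can decide whether the 85% goal is met.

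**The case against.** The strongest answer is that Section 4.8 means something narrower. It also uses the term for what participants are paid for, and the Subject Status form in Appendix C has incentive fields for the baseline assessment, the post-test assessment and the interview, while the attendance form has none. That suggests, without proving it, that the term there means the assessments. Section 7 fits this reading: "Participants will be asked to attend all four sessions as is possible". So does the 75% attendance goal in Section 6.1, since missed sessions are expected. On this reading a person who can still do the survey and call is not withdrawn. This stands as a possible reading, but the text does not settle it, and two staff members could apply the rule differently.

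A reader might infer that acceptability would go unmeasured in these people. The documents do not support that. Section 2.1 counts the credibility measure toward acceptability and satisfaction, and Appendices A and B place it at session 2, so it may already be in hand. Daily reports, reasons for missed sessions, the withdrawal reason and the adverse event form also keep short accounts. What they do not hold is the satisfaction item or the interview.

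A reader might also infer that the rule removes those who tolerated the course worst. It covers any adverse event, and Appendix C allows for definitely unrelated ones. People who simply dislike the course would more naturally withdraw by choice, which the remedy does not address.

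Nor does the plan forbid contact after withdrawal; that no post-test is offered is an inference from its silence. Loss of adverse event outcomes is not shown either: Sections 4.5 and 9 allow follow-up with no end date, and the form has end and outcome fields.

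**Conclusion.** The point holds at low severity. On the protocol's only listing of study procedures, Section 4.8 withdraws a participant whose event stops only the sessions or home practice, and the plan then provides no route to the two contacts that collect the satisfaction item, barriers and suggestions.

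The numbers are small: 0.24 to 2.4 people expected under assumed chances of 1% to 10%, and an overstatement of 0 to 7.7 points for one or two people, inside a half-width of about 16. The event rates and the 85% satisfaction are assumptions, because the documents give neither. A claim that the reported percentage would be materially biased is therefore not supported. The loss is mainly interview content on why someone stopped, which can matter in a feasibility study with about 20 interviews and is cheap to protect.

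**What to change.** Replace the adverse event sentence in Section 4.8 with wording such as:

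> If an adverse event prevents a participant from attending sessions or doing home practice, the investigators decide, as in Section 9, whether those components stop. Unless consent is withdrawn, the participant remains in the study, is offered the post-test survey and phone interview at the planned time, and known adverse events continue to be followed under Section 9.

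Set no cut-off for adverse event follow-up at the post-test window. Report the number of event-related session discontinuations beside retention, so that a tolerability problem stays visible when these people count as retained.

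The cost is one sentence and one reported count. No new form, column or measure is needed, because the attendance notes and the action and outcome fields of the adverse event form can record this state, and the sample size is unchanged. There are two downsides: retention can rise by up to 4.2 points per such person, and an affected participant receives a few extra contacts, which may be declined.

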4.9 Screen failure procedures

Individuals who are deemed ineligible during the phone screen will be informed by the screener that they are not eligible and thanked for their time. The screener will provide a reason for exclusion if requested by the individual.

5 STUDY EVALUATIONS AND MEASUREMENTS (how measurements will be made)

All study evaluations and measurements will be made via the following methods: 1) Participant self-report (online survey questionnaires, phone screening, phone interview, adverse experience/event reporting during or between sessions), 2) Behavioral observation of instructor fidelity to the intervention protocol during intervention sessions, and 3) documentation of feasibility variables, including participants' session attendance, survey completion, enrollment and withdrawal. No variables will be abstracted from medical charts. See **Appendix C** for all self-report measures included and **Appendix D** for case report forms.

5.1 Efficacy Evaluation (if applicable)

Not applicable – this is a feasibility study and is not designed or powered to test efficacy of the intervention

5.2 Pharmacokinetic Evaluation (if applicable)

Not applicable

5.3 Safety Evaluations

Participants will be asked to report on any unwanted reactions to the mindfulness skills practice. Reports will be collected via online surveys daily when collecting home practice data. Observations will be made during intervention sessions.

6 STATISTICAL CONSIDERATION

A repeated-measures single group design will be used to test the feasibility and acceptability of the intervention. The study is not powered to test efficacy or significant changes in secondary outcome measures. There is no control group, as the research question pertains to feasibility and acceptability of the mindfulness skills group.

6.1 Primary Endpoint

The primary outcomes are feasibility and acceptability of the intervention and study procedures. Feasibility will be assessed as 1) ability to enroll 12 participants for one intervention group within 4-6 weeks, 2) participant retention, with a goal of 85% retention, 3) session attendance, with a goal of 75% sessions attended, 4) proportion of completed assessments and practice forms.

Acceptability will be assessed via credibility questionnaire and semi-structured interview assessing satisfaction with the intervention, barriers to engagement, and suggestions for improving the intervention or study procedures.

6.2 Secondary Endpoint

Secondary outcomes will all be measured via self-report and include 1) PROMIS-29 adult profile measuring physical functioning and health-related quality of life domains, pain intensity/interference, anxiety and depressive symptoms, 2) psychological variables including pain acceptance, pain catastrophizing, positive affect, emotional/behavioral self-regulation, and mindfulness. Adverse events will be evaluated via self-report, and participants will have the opportunity to report adverse events during intervention sessions, and by contacting study staff at any time during participation in the study.

6.3 Statistical Methods

Quantitative Analyses: Baseline demographic, pain medication use, and pain condition variables will be characterized using means and percentages and their standard deviations. Primary feasibility/acceptability outcomes will be analyzed using percentages (proportions) and 95% confidence intervals (CIs). Secondary outcomes will be analyzed by using paired t-tests and examining the pre/post intervention change in scores and their respective standard errors with 95% confidence intervals. Influence of the pretest score on change (i.e., ceiling and floor effects) will be investigated.

Qualitative Analyses: The qualitative description method will be used for interview data.²⁶ Major themes within the content will be identified and a codebook created. A test sample of interviews will be coded and the codebook refined, followed by coding remaining interviews. The outcome will be a descriptive summary of the contents of the data.

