	(3) Intervention : Four weekly, 1 hour 30 minute group mindfulness training sessions co-facilitated by an experienced mindfulness instructor (Faculty advisor [name]) and a clinical psychologist with pain psychology training (PI [name]).					
	(4) Post-measures: Within 1-2 weeks after intervention, administered via online self-report questionnaires and with semistructured phone interview.					
Efficacy Evaluations	Feasibility and acceptability will be measured with 1) enrollment statistics, 2) study retention, 3) assessment completion, 4) session attendance, 4) home practice diaries, and 5) credibility questionnaire and semi-structured phone interviews assessing participant satisfaction. Secondary outcomes will be measured with self-report questionnaires.					

Pharmacokinetic Evaluations	N/A
Safety Evaluations	Participant self-report of adverse experiences in response to mindfulness meditation practice. Will assess during intervention sessions. Will monitor AEs/SAEs that may or may not be study related as reported by participants.
Statistical And Analytic Plan	Primary feasibility/acceptability outcomes will be analyzed using percentages and 95% CIs. The qualitative description method will be used for interview data by identifying major themes within the content and producing a descriptive summary of the data. Secondary outcomes will be analyzed using paired t-tests and by examining the pre/post intervention change in scores and their respective standard errors with 95% confidence intervals.
Data And Safety Monitoring Plan	The PI ([name]) is responsible for data quality management and ongoing assessment of participant safety. The faculty advisor ([name]) will advise PI [name] on issues of data quality management and assessment of safety.

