4.3 Intervention procedures (by visits)

The mindfulness intervention will consist of four, weekly group mindfulness skills sessions each lasting 1 hour and 30 minutes. Each session will allow time for a 5-minute break in the middle. Sessions will be co-instructed by PI [name] and faculty advisor [name]. All sessions will take place at the same location. See **Appendix B** for session-by-session content and home practice assignments. Participants will receive guided audio recordings for mindfulness skills practice, in addition to a binder with course handouts. The instructor will send one email to each participant the day after each session summarizing the session content and home practice assignments and encouraging participants to complete the daily mindfulness practice diaries. Sessions will be recorded to monitor fidelity to the intervention protocol. Participants will be asked to complete daily home practice and pain intensity diaries between session weeks 1 and 4 via online REDCap surveys that will be sent by email on a daily basis.

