6.4 Sample Size and Power

Anticipating a participant retention proportion of 0.85, the estimated half-width of a 95% CI for the proportion based on 24 enrolled participants is 0.14, which would give a CI of (0.71,0.99). Assuming the overall proportion of sessions attended is 0.75 and an intra-participant correlation of 0.10, the estimated half-width of a 95% CI for the proportion out of a total of 96 possible participant-sessions is 0.10, which would give a CI of (0.65,0.85). Assuming a 15% dropout rate, a sample size of 20 across two groups at post-test is adequate to estimate the feasibility and to generate preliminary data for planning a larger trial.

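### Does practice-form completion need a stated denominator and interval method in section 6.3?

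*Combined protocol and SAP*

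**What the plan says.** Section 6.1 lists four feasibility outcomes. The fourth is the "proportion of completed assessments and practice forms". Enrolment, retention and attendance each come with a goal; this one does not.

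Section 6.3 covers all of them in one sentence: "Primary feasibility/acceptability outcomes will be analyzed using percentages (proportions) and 95% confidence intervals (CIs". The synopsis repeats it: "Primary feasibility/acceptability outcomes will be analyzed using percentages and 95% CIs".

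The number of forms has to be inferred. Section 4.3 says "Participants will be asked to complete daily home practice and pain intensity diaries between session weeks 1 and 4", and Appendix A marks the first interval as "daily from W1- 2", followed by weeks 2 to 3 and 3 to 4. Three weeks of daily forms make about 21 per participant.

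Section 6.4 works through two outcomes only: retention on 24 enrolled, and attendance, where "the proportion out of a total of 96 possible participant-sessions is 0.10" at a within-participant correlation of 0.10. It also plans for losses: "Assuming a 15% dropout rate, a sample size of 20 across two groups at post-test". On withdrawal, section 4.8 says "Should a participant choose to withdraw from the study for any reason, their withdrawal will be documented in the case report form".

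**The concern.** Practice forms have the most repeated records per person of any outcome in the study, yet they are the repeated outcome for which section 6.4 gives neither a denominator nor a correlation. Two analysts could both follow section 6.3 and report different results. One might divide by every scheduled form, the other by forms sent before withdrawal. One might treat some 500 forms as independent, the other might treat the participant as the unit.

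The first choice moves the percentage; the second can make the interval much too narrow. Feasibility is the primary objective, online data collection is named in it, and the results are meant to inform a larger trial. A misleadingly precise completion rate would therefore be carried forward.

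**Working it through.** **1. The plan's own figures.** Half-width = 1.96 × √[p(1−p) × DE / N], with design effect DE = 1 + (m−1) × ICC, where m is the number of records per person and ICC the within-participant correlation.

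- Retention (p = 0.85, N = 24, DE = 1): 1.96 × √(0.1275/24) = 0.143. Section 6.4 states 0.14.
- Attendance (p = 0.75, N = 24 × 4 = 96, ICC = 0.10, DE = 1 + 3 × 0.10 = 1.3): 1.96 × √(0.1875 × 1.3/96) = 0.0988. Section 6.4 states 0.10.
- Attendance without the correlation: 1.96 × √(0.1875/96) = 0.087.

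The attendance figure rounds to 0.10 only with the correlation, so the planners did allow for repeated records within a person.

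**2. Inputs for practice forms.** From the plan: 24 enrolled, 20 at post-test, 15% dropout. Inferred: 21 forms each, so 24 × 21 = 504. Assumed, because the documents give no figure: 75% completion while active, none after dropout, and the correlations and dropout times below.

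**3. Denominator.** With 4 participants leaving after d days, completion over all scheduled forms is 0.75 × (20 × 21 + 4d)/504.

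| Dropouts leave after | All scheduled forms | Forms sent |
|---|---|---|
| 0 days | 0.75 × 420/504 = 62.5% | 75% |
| 7 days | 0.75 × 448/504 = 66.7% | 75% |
| 14 days | 0.75 × 476/504 = 70.8% | 75% |

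The difference is 4.2 to 12.5 percentage points. The top row is extreme, since all four leave before the first form.

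**4. Interval, no dropout.** Pooled as independent, the half-width is 1.96 × √(0.1875/504) = 0.038. Coverage is from 40,000 simulated studies per scenario.

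| ICC | DE | Correct half-width | Coverage if pooled as independent |
|---|---|---|---|
| 0 | 1.0 | 0.038 | 0.95 |
| 0.01 | 1.2 | 0.041 | 0.92 |
| 0.05 | 2.0 | 0.054 | 0.84 |
| 0.10 | 3.0 | 0.065 | 0.74 |

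The form count matters little: at ICC 0.10 the half-width is 0.066 with 20 forms each and 0.063 with 28.

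**5. Interval, 15% dropout, days otherwise independent.** Here all scheduled forms are the denominator and forms after dropout count as missed. If dropouts leave at day 0, mean completion is 0.85 × 0.75 = 0.6375. The between-person variance is 0.75² × 0.85 × 0.15 = 0.0717, so ICC = 0.0717/(0.6375 × 0.3625) = 0.310 and DE = 1 + 20 × 0.310 = 7.2. The later cases are simulated.

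| Dropouts leave after | DE | Coverage, pooled | Coverage, participant-level t interval |
|---|---|---|---|
| 0 days | 7.2 | 0.52 | 0.92 |
| 7 days | 3.8 | 0.69 | 0.93 |
| 14 days | 1.7 | 0.87 | 0.95 |

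With forms sent as denominator in the same scenarios, pooled coverage is 0.947 to 0.949. In this table the loss of coverage comes from combining one denominator with one interval method, and the plan specifies neither.

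**6. What the records allow.** The calendar fixes the number of scheduled forms. Section 10 gives each participant unique survey links, so completions can be attributed to a person. Withdrawal goes on the case report form, which has columns for status, reason and study completion date but no separate withdrawal date. The forms-sent version therefore relies on a date being entered there or on the survey system's own record. Subject to that, both denominators look recoverable afterwards.

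**The case for a change.** The strongest argument for a change is that form completion belongs to the primary outcomes and section 6.3 promises it an interval. Two sentences would remove the ambiguity. Appendix A does call the daily diaries exploratory, but that label fits their content (practice and pain) better than their completion, so it does not dispose of the point. Nor does the interval problem depend on dropout. People who keep diaries regularly tend to go on doing so, and a correlation of 0.10 among forms already takes pooled coverage to 0.74 whichever denominator is used.

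It can also be said that section 6.4 does not settle the analysis even for attendance. The 0.10 correlation and the 96 participant-sessions are sample-size assumptions. Section 6.3 does not carry the correlation forward, and no section says that sessions after withdrawal stay in the denominator.

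All of this stands as a description of what is unwritten. It does not show an error. Pooling as independent would be the analyst's mistake, not an instruction in the plan, and section 6.4 points the other way. There is also no single right denominator to prescribe: all scheduled forms measures the yield of the procedure, and forms sent measures adherence among those still taking part. A feasibility report can give both. Nor is the obvious interval perfect: with 90% active completion and evenly spread 15% dropout, the participant-level t interval covers 0.89, against 0.56 pooled.

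**Conclusion.** This is missing detail that an analyst can fill sensibly, and no change to the plan is needed. It affects one descriptive percentage with no goal attached, in a study of 24 people that tests no hypothesis on it. The sample size, the retention and attendance figures in section 6.4 and the goals in section 6.1 are all untouched.

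On the assumptions above (21 forms, 75% active completion, 4 of 24 lost), the denominator moves the percentage by 4.2 to 12.5 points. Ignoring a correlation of 0.10 would shrink the half-width from 0.065 to 0.038. Neither shift alters a conclusion that the plan draws. The conclusion rests on two conditions: that the report names the denominator it used, and that the interval treats the participant as the unit, in line with the way section 6.4 planned attendance.
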